12.2 Appendix 2: Liver Safety Monitoring and Assessment

If laboratory testing for a subject enrolled in study and receiving study drug reveals an increase in serum aminotransferases (AT) to $>3X$ ULN, bilirubin $> 2 \times$ ULN, at least all four of the usual serum hepatic measures (ALT, AST, ALP, and TBL) must be repeated. Testing should be repeated within 48-72 hours of notification of the test results. Alerts will be generated by the central lab regarding moderate and severe liver abnormality to inform the Investigator, study monitor and study team. Subjects should be asked if they have any symptoms suggestive of hepatobiliary dysfunction.

Definition of Liver Abnormalities

Confirmed abnormalities will be characterized as moderate and severe where ULN:

Moderate	ALT or AST $> 3 \times$ ULN	or	Total Bilirubin $> 2 \times$ ULN
Severe*	$> 3 \times$ ULN	and	$> 2 \times$ ULN

In addition, the subject should be considered to have severe hepatic abnormalities for any of the following:

- ALT or AST $> 8 \times$ ULN
- ALT or AST $> 5 \times$ ULN for more than 2 weeks
- ALT or AST $> 3 \times$ ULN and INR > 1.5 (If INR testing is applicable/evaluated).
- ALT or AST $> 3 \times$ ULN with the appearance of fatigue, nausea, vomiting, right upper quadrant pain or tenderness, fever, rash and/or eosinophilia ($> 5\%$).

The Investigator may determine that abnormal liver function results, other than as described above, may qualify as moderate or severe abnormalities and require additional monitoring and follow-up.

Follow-up Procedures

Confirmed moderate and severe abnormalities in hepatic functions should be thoroughly characterized by obtaining appropriate expert consultations, detailed pertinent history, physical examination and laboratory tests. The site should complete the Liver Abnormality Case Report Form (LA-CRF) or an appropriate document. Subjects with confirmed abnormal liver function testing should be followed as described below.

Confirmed moderately abnormal LFTs should be repeated 2-3 times weekly then weekly or less if abnormalities stabilize or the study drug has been discontinued and the subject is asymptomatic.

Severe hepatic liver function abnormalities as defined above, in the absence of another etiology, may be considered an important medical event and may be reported as a Serious Adverse Event (SAE). The Sponsor should be contacted and informed of all subjects for

whom severe hepatic liver function abnormalities possibly attributable to study drug are observed.

To further assess abnormal hepatic laboratory findings, the Investigator is expected to:

- Obtain a more detailed history of symptoms and prior or concurrent diseases. Symptoms and new onset-diseases should be recorded as ‘adverse events’ on the AE page of the (e)CRF. Illnesses and conditions such as hypotensive events, and decompensated cardiac disease that may lead to secondary liver abnormalities should be noted. Non-alcoholic steatohepatitis (NASH) is seen in obese hyperlipoproteinemic, and/or diabetic patients and may be associated with fluctuating aminotransferase levels. The Investigator should ensure that the medical history form captures any illness that pre-dates study enrollment that may be relevant in assessing hepatic function.
- Obtain a history of concomitant drug use (including non-prescription medication, complementary and alternative medications), alcohol use, recreational drug use, and special diets. Medications, including dose, should be entered on the concomitant medication page of the (e)CRF. Information on alcohol, other substance use, and diet should be entered on the LA-CRF or an appropriate document.
- Obtain a history of exposure to environmental chemical agents.
- Based on the subject’s history, other testing may be appropriate including:
 - acute viral hepatitis (A, B, C, D, E or other infectious agents)
 - ultrasound or other imaging to assess biliary tract disease
 - other laboratory tests including INR, direct bilirubin
- Consider gastroenterology or hepatology consultations.
- Submit results for any additional testing and possible etiology on the LA-CRF or an appropriate document.

Study Discontinuation

In the absence of an explanation for increased LFT’s, such as viral hepatitis, pre-existing or acute liver disease or exposure to other agents associated with liver injury, the subject may be discontinued from the study. The Investigator may determine that it is not in the subject’s best interest to continue study enrollment. Discontinuation of treatment should be considered if:

- ALT or AST > 8 × ULN
- ALT or AST > 5 × ULN for more than 2 weeks
- ALT or AST > 3 × ULN and TBL > 2 × ULN or INR > 1.5) (If INR testing is applicable/evaluated)
- ALT or AST > 3 × ULN with the appearance of fatigue, nausea, vomiting, right upper quadrant pain or tenderness, fever, rash and/or eosinophilia (> 5%).

Reference

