5.5.2 Definition of Serious Adverse Events (SAEs)

An adverse event is considered “serious” if, in the view of either the Investigator or Sponsor, it results in any of the following outcomes:

- Results in death
- Is life threatening (an adverse event is considered “life-threatening” if, in the view of either the Investigator or Sponsor, its occurrence places the subject at immediate risk of death. It does not include an adverse event that, had it occurred in a more severe form, might have caused death)
- Results in persistent or significant disability/incapacity or substantial disruption of the ability to conduct normal life functions
- Results in congenital anomaly, or birth defect
- Requires inpatient hospitalization or leads to prolongation of hospitalization (hospitalization for treatment/observation/examination caused by AE is to be considered as serious)
- Other medically important events.

Medical and scientific judgment should be exercised in deciding whether expedited reporting is appropriate in other situations, such as important medical events that may not be immediately life-threatening or result in death or hospitalization but may jeopardize the subject or may require intervention to prevent one of the other outcomes listed in the definition above. These events, including those that may result in disability/incapacity, should also usually be considered serious. Examples of such events are intensive treatment in an emergency room or at home for allergic bronchospasm; blood dyscrasias or convulsions that do not result in hospitalization; or development of drug dependency or drug abuse. Stroke, myocardial infarction, dysrhythmias, and uncontrolled hypertension will also be examined.

In addition to AEs special situations (SS) (with or without an associated AE) occurring on the medicinal products administered to the subject as part of the study (e.g., study drug, comparator, background therapy) that may require expedited reporting and/or safety evaluation include, but are not limited to:

- Overdose of the medicinal product(s)
- Suspected abuse/misuse of the medicinal product(s)
- Inadvertent or accidental exposure to the medicinal product(s)

- Medication error involving the medicinal product(s) (with or without subject/patient exposure to the Sponsor medicinal product, e.g., name confusion)

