5.5.5 Reporting of Serious Adverse Events (SAEs)

The reference safety information for mirabegron to be used for this study is the Company Core Data Sheet (CCDS) for mirabegron, Section 4.8- Undesirable Effects.

Please refer to the reference safety information for details of prescribing information (contraindications, special warnings and precautions).

In the case of a serious adverse event (SAE), the Investigator must contact the Sponsor by telephone or fax immediately (within 24 hours of awareness).

The Investigator should complete and submit an SAE Worksheet containing all information that is required by the Regulatory Authorities to the Sponsor by fax immediately (within 24 hours of awareness). If the faxing, scanning or emailing of an SAE Worksheet is not possible within 24 hours, the local drug safety contact should be informed by phone. Please fax the SAE Worksheet to:

Astellas Pharma Global Development, Inc. – United States
Product Safety & Pharmacovigilance
North America telefax numbers: [REDACTED]
International telefax number: [REDACTED]
Email: [REDACTED]

If there are any questions, or if clarification is needed regarding the SAE, please contact the Sponsor's Medical Monitor/Expert or his/her designee (see Section II Contact Details of Key Sponsor's Personnel).

Follow-up information for the event should be sent promptly (within 7 days of the initial notification).

Full details of the SAE should be recorded on the medical records and on the eCRF.

The following minimum information is required:

- ISN/Study number,
- Subject number, sex and age,
- The date of report,
- A description of the SAE (event, seriousness of the event)
- Causal relationship to the study drug.

The Sponsor or Sponsor's designee will submit expedited safety reports (i.e., IND Safety Reports) to the regulatory agencies (i.e., FDA) as necessary, and will inform the Investigators of such regulatory reports. Investigators must submit safety reports as required by their Institutional Review Board (IRB)/Independent Ethics Committee (IEC) within timelines set by regional regulations (i.e., EU, (e)CTD, FDA). Documentation of the submission to and receipt by the IRB/IEC of expedited safety reports should be retained by the site.

The Sponsor or Sponsor's designee will notify all Investigators responsible for ongoing clinical studies with the study drug of all SAEs which require submission per local requirements to the IRB/IEC/head of the study site.

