12.3 Appendix 3: Common Serious Adverse Events

For this protocol, there is no list of common serious adverse events that the Sponsor considers to be associated with the disease state being studied for which a single occurrence will be excluded from IND safety reporting. All SAEs should be reported.

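### Appendix 2 makes the seriousness of a severe liver abnormality depend on its cause and makes SAE reporting optional, against Sections 5.5.2, 5.5.3, 5.5.5 and Appendix 3

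*Protocol*

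**What the plan says.** Appendix 2 (12.2) defines a class of severe hepatic abnormalities, for example ALT or AST above 3x ULN together with total bilirubin above 2x ULN, or ALT or AST above 8x ULN. Under Follow-up Procedures it says that such an abnormality, "in the absence of another etiology, may be considered an important medical event and may be reported as a Serious Adverse Event (SAE". The sentence that follows limits informing the Sponsor to severe cases that may be attributable to study drug.

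Section 5.5.2 calls an event serious if, "in the view of either the Investigator or Sponsor, it results in any of the following outcomes", and the list ends with "Other medically important events". It adds: "Medical and scientific judgment should be exercised in deciding whether expedited reporting is appropriate in other situations", naming important medical events as an example, and says of these: "These events, including those that may result in disability/incapacity, should also usually be considered serious".

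Section 5.5.3 grades causal relationship separately, and Section 5.5.5 lists that grade among the minimum items of an SAE report. For an SAE, 5.5.5 states that "the Investigator must contact the Sponsor by telephone or fax immediately (within 24 hours of awareness". Appendix 3 (12.3) exempts no event from this: "All SAEs should be reported".

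Section 5.4 separately requires the Sponsor to be contacted within 24 hours about a confirmed *marked* hepatic abnormality, referring to Appendix 2 for the definition.

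**The concern.** Seriousness and causality are two different judgements, and the main text keeps them apart. Appendix 2 joins them for one class of event, so an opinion on cause decides whether the event is serious at all. It then makes reporting permissive where the main text makes it a duty.

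What is at stake is whether the SAE summaries by treatment group (7.5.1) mean the same thing at every site. Severe liver cases are few in most trials of this size, though the protocol gives no expected rate. With few cases, a difference in classification shows directly in the table. The study may use up to 100 centers (2.2.1) and has no data monitoring committee (10.1), so consistency rests mainly on the written rule and on the Sponsor's own review.

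**Working it through.** No arithmetic applies: no rate, error level or sample size enters the point. The check sets the passages side by side.

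| Question | Main text | Appendix 2 |
|---|---|---|
| Does cause affect seriousness? | No. 5.5.2 lists outcomes only. | Yes. Another etiology removes the case from the sentence. |
| Where is cause recorded? | 5.5.3 grade, sent with the SAE report (5.5.5). | It acts as a condition for SAE status. |
| Is an important medical event serious? | Listed as serious; by default it "should also usually be considered serious". | It *may* be considered an important medical event; no default is given. |
| Once it is an SAE, is it reported? | Yes, a duty (5.5.5, Appendix 3). | It *may* be reported. |
| When is the Sponsor contacted? | 5.4: confirmed *marked* abnormality, no condition on cause. | Severe cases possibly due to study drug; *marked* is not among its classes, which are moderate and severe. |

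**The etiology condition.** Nothing in 5.5.2 allows cause to enter the decision. The judgement clause there does not mention it. This is the firmest part of the conflict.

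**The first *may*.** Whether a laboratory abnormality is an important medical event is a matter of judgement under 5.5.2 as well. This *may* is consistent with the main text.

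**The second *may*.** Suppose the case has been considered an important medical event. The 5.5.2 list then makes it serious, and 5.5.5 makes reporting a duty. Optional reporting at this stage cannot be squared with that.

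**A worked case.** Take a man with ALT above 3x ULN and bilirubin above 2x ULN who is not in hospital and meets no other 5.5.2 criterion.

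- Site A finds another etiology, for example steatohepatitis, and follows Appendix 2: not an SAE.
- Site B has the same findings and follows 5.5.2. It judges the event medically important, reports an SAE and grades causality as not related.
- Site C finds no other etiology, considers the event medically important and uses the second *may*: not reported as an SAE.

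All three can point to protocol text.

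**Where the case still appears.** The Section 6.1 list of criteria for discontinuing a subject covers every specific severe criterion in Appendix 2 except ALT or AST above 3x ULN with INR above 1.5. An abnormality that requires discontinuation of study medication is an adverse event (5.5.1). Section 7.5.1 tabulates adverse events leading to discontinuation and lists all adverse events. Section 7.5.2 adds shift tables using the most extreme value on treatment. Appendix 2 provides central laboratory alerts to the investigator, monitor and study team, and asks for the Liver Abnormality Case Report Form (LA-CRF) or an equivalent document.

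**The case against.** The strongest reply is that discretion over important medical events is already in the main text. Section 5.5.2 asks for judgement on whether expedited reporting is appropriate for them, and its default is qualified by *usually*. The duty in 5.5.5 and Appendix 3 applies only once an event is an SAE; it does not turn a laboratory threshold into one. This stands for the first *may*. It also means that some variation between sites would remain without Appendix 2. It does not explain the etiology condition. For the second *may* it helps little, because 5.5.2 sets a default in favour of seriousness and Appendix 2 sets none.

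The second reply is that safeguards exist. Either the Investigator or the Sponsor can judge an event serious. The Sponsor receives laboratory alerts and keeps a list of events it always treats as serious (5.5.2). A case with hospitalization, threat to life or death is an SAE whatever Appendix 2 says. All of this stands and limits the harm.

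A reader might therefore infer too much in two ways. One inference is that severe liver cases vanish from the safety data on one site's opinion. The documents do not support that, given the Sponsor's own right to classify and the other tables and listings. The other is that every severe laboratory finding must be an SAE. Section 5.5.2 does not say so; it leaves room for judgement.

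**Conclusion.** The point holds as a contradiction in reporting rules. Appendix 2 makes seriousness conditional on cause and makes reporting optional for a case already considered an important medical event; 5.5.2, 5.5.3, 5.5.5 and Appendix 3 do neither. The consequence is inconsistent SAE classification and counts across sites, and possibly differences in when SAE reports are made, rather than loss of the cases.

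No numerical size can be attached, since the protocol states no expected hepatic event rate. Sites are blinded (4.4.1), so nothing in the wording itself favours one arm.

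The conclusion assumes that sites apply Appendix 2 as written and that the case meets no other seriousness criterion. The statement that most cases remain visible as discontinuations assumes that the 6.1 criteria are applied. Appendix 2 words stopping more loosely than 6.1, and those passages also need to be reconciled; no view is taken here on which is right.

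**What to change.** Reconcile the Appendix 2 sentence with the main text by deleting the etiology condition and replacing the rest along these lines: *A severe hepatic abnormality is assessed for seriousness under 5.5.2 whatever its suspected cause. If it is judged an important medical event, it is reported as an SAE under 5.5.5. Any alternative etiology is recorded under causality (5.5.3) and on the LA-CRF.* This keeps the judgement that 5.5.2 allows and removes only what contradicts it.

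At the same time, make the two sponsor-contact rules agree. Either define *marked* in Appendix 2 or replace it in 5.4 with one of the defined classes, and state in both places whether contact depends on possible attribution to study drug.

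The cost is a few sentences in an amendment and a few more SAE reports, some of which will be graded as not related. The LA-CRF already takes possible etiology, so no new data item is needed.

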12.3 Appendix 3: Common Serious Adverse Events

For this protocol, there is no list of common serious adverse events that the Sponsor considers to be associated with the disease state being studied for which a single occurrence will be excluded from IND safety reporting. All SAEs should be reported.

12.4 Appendix 4: Investigator Criteria for Hypertension

Investigator Criteria for Determining TEAE of Hypertension

During each office visit a systolic and diastolic blood pressure will be measured. The Investigator responsibility for reporting the TEAE of hypertension will be based on office visit measurements and not on diary review.

For post-baseline assessments, the Investigator will use the following criteria, as defined in the protocol, to determine if a subject is considered hypertensive:

An AE of hypertension will be recorded if one of the following criteria is met on 2 consecutive visits:

1. If the average systolic blood pressure is ≥ 140 mmHg AND/OR the average diastolic blood pressure is ≥ 90 mmHg at two consecutive visits after Baseline (Visit 2) in subjects who were normotensive (average systolic blood pressure < 140 mmHg and average diastolic blood pressure < 90 mmHg [WHO-ISH, 2013]) at Baseline (Visit 2).
2. If the average systolic blood pressure is increased >20 mmHg AND/OR the average diastolic blood pressure is increased > 10 mmHg at two consecutive visits as compared to Baseline (Visit 2) in subjects with hypertension at Baseline (Visit 2).
3. If treatment with antihypertensive drugs is initiated for treatment of hypertension or if the dose of prior antihypertensive drugs is increased due to an increase in blood pressure.

In addition, the Investigator can record an AE based on clinical assessment.

12.5 Appendix 5: Investigator Criteria for Tachycardia

Investigator Criteria for Determining TEAE of Tachycardia

During each office visit pulse rate will be measured. The Investigator responsibility for reporting the TEAE of tachycardia will be based on office visit measurements and not on diary review. Tachycardia is defined as a resting heart frequency > 100 beats per minute (bpm) measured as pulse rate. If pulse rate is > 100 bpm at the office visit, the Investigator is to record an AE of tachycardia. However, if the Investigator's clinical assessment was that this did not constitute an AE of tachycardia, then an AE will as not be recorded.

13 ATTACHMENT 1: SUBSTANTIAL AMENDMENT 4

I. The purpose of this amendment is:

Substantial Changes
1. Updated Reference Safety Information (RSI)
DESCRIPTION OF CHANGE:
Revised RSI from the US Package Insert, Canadian Monograph, and SmPC to the Company Core Data Sheet for mirabegron.
RATIONALE:
Astellas Pharmacovigilance (PV) refers to the Company Core Data Sheet for mirabegron as the physical reference for RSI. There is no change in the risk to patients or what safety information is reported with this update to the protocol. This update provides consistency of RSI with PV and the protocol.

II. Amendment Summary of Changes:

Substantial Changes:

1. Updated Reference Safety Information (RSI)
Page 58, 5.5.5 Reporting of Serious Adverse Events (SAEs)
WAS:
The reference safety information for mirabegron to be used for this study is the US Package Insert for the US, EU SmPC for EU countries and the Canadian Monograph for Canada. The reference safety information is equal in each document.
IS AMENDED TO:
The reference safety information for mirabegron to be used for this study is the Company Core Data Sheet (CCDS) for mirabegron, Section 4.8 Undesirable effects. US Package Insert for the US, EU SmPC for EU countries and the Canadian Monograph for Canada. The reference safety information is equal in each document.

1. Updated Reference Safety Information (RSI)
Page 77, 11 References
ADDED:
Company Core Data Sheet for mirabegron.

